### 10.1.2. List of Graphs

- Boxplots of baseline AUC day3-21 by lab, sex at birth, tissue type, and virus, treatment arms combined
- Boxplots of baseline AUC day3-21 by lab, sex at birth, tissue type, virus, visit, and treatment arm
- Lineplots of post-baseline AUC day3-21 by lab, sex at birth, tissue type, and virus, treatment arms combined
- Lineplots of post-baseline AUC day3-21 by lab, sex at birth, tissue type, virus, and treatment arm
- Scatterplots of rectal vs. cervical AUC day3-21 by virus, visit and treatment arm for female participants
- Scatterplot of rectal vs. vaginal AUC day3-21 by virus, visit and treatment arm for female participants
- Scatterplot of cervical vs. vaginal AUC day3-21 by virus, visit and treatment arm for female participants
- Scatterplot of male rectal vs. female rectal AUC day3-21 by virus, visit and treatment arm

## 10.2. Mucosal VRC01/LS Level

### 10.2.1. List of Tables

- Summary statistics (i.e., min, mean, median, max, standard deviation, IQR) of VRC01/LS concentration normalized by total IgG and protein, by tissue type, visit, and treatment arm.
- Summary statistics (i.e., min, mean, median, max, standard deviation, IQR) of total IgG and protein, by tissue type, visit, and treatment arm.
- Summary statistics (i.e., min, mean, median, max, standard deviation, IQR) of VRC01/LS concentration without normalization, by tissue type, visit, and treatment arm.

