9.6 Mucosal sampling

Mucosal secretion and biopsy samples will be collected at the timepoints indicated in [Appendix L](#), [Appendix M](#), [Appendix N](#), and [Appendix O](#). All participants in this trial will have consented to mucosal specimen collections. Participants born male will provide semen, rectal fluids, and rectal biopsies. Participants born female will provide cervicovaginal fluids, as well as cervical and vaginal biopsies. At the Seattle CRS, female participants will also provide rectal fluids and rectal biopsies, if they agree to do so. Small (~2-4 mm) tissue biopsies are obtained from the vagina and cervix using a speculum and from the rectum by anoscopy by experienced clinicians. The number of biopsies per mucosal compartment and visit is described in detail in [Table 9-1](#) and [Table 9-2](#), and also outlined in [Appendix H](#), [Appendix I](#), [Appendix J](#), and [Appendix K](#), however fewer samples may be taken based on the judgment of the performing clinician. If a female participant is no longer willing to provide cervicovaginal specimens, a switch to the rectal compartment is possible. During the trial, a participant may decline all or some of the mucosal biopsies or secretion collections, but they should be encouraged to continue with any collections that they deem acceptable until the end of the trial.

Table 9-1 Mucosal biopsy collection schedule for Groups 1-3

Tissue	Function	Visit 2 (Baseline)	Visit 14 (Month 6)	Visit 15 (Month 7)	Visit 16 (Month 9)	Visit 17 (Month 12)	Visit 18** (Month 15)	Visit 19** (Month 18)
Rectal # of Bx and Use	Ab levels	1	1	1	1	1	1	1
	IHC	1	1	1	1	1	1	1
	Infectivity	3	3	3	3	3	3	3
	Total = 35*/25	5	5	5	5	5	5	5
Ectocervical # of Bx and Use	Ab levels	1	1	1	1	1	1	(1)***
	IHC	1	1	1	1	1	1	(1)***
	Infectivity	2	2	-	-	-	-	-
	Total = 16*/14	4	4	2	2	2	2	(2)***
Vaginal # of Bx and Use	Ab levels	1	1	1	1	1	1	(1)***
	IHC	1	1	1	1	1	1	(1)***
	Infectivity	3	3	3	3	(3)***	(2-3)***	(2-3)***
	Total = 24*/22	5	5	5	5	2 [(5)***]	2 [(4-5)***]	(2-5)***

* Number of samples refers to Group 3

** Visits only apply to group 3

*** These samples will only be collected if the participant has missed prior collection visit(s), in order to maintain the total number of biopsies indicated in the "Function" column.

Table 9-2 Mucosal biopsy collection schedule for Groups 4-5

Tissue	Function	Visit 4 (0 mo)	Visit 5 (1 mo)	Visit 9 (3 mo)	Visit 12 (4.5 mo)	Visit 14 (6 mo)	Visit 16** (9 mo)	Visit 17** (12 mo)

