### 3. OBJECTIVES AND ENDPOINTS

#### 3.1. Primary objective:

*Primary objective 1:*

- To evaluate the safety and tolerability of VRC01/VRC01LS mAb administered through IV infusion.

*Primary endpoints 1:*

- Local and systemic reactogenicity, laboratory measures of safety, AEs, SAEs, and rates of discontinuation.

*Primary objective 2:*

- For each sex at birth, to evaluate the pharmacokinetics of VRC01 in serum versus mucosa in each mucosal compartment.

*Primary endpoint 2 (Groups 1 & 2 & 4):*

- Serum concentration of VRC01 out to Month 6 after the last infusion.
- Levels of VRC01 in genital and rectal secretions, as well as cervical, vaginal, and rectal tissues at the collection timepoints.

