### **8.5. Analyses of mAb concentration and functional responses**

#### **8.5.1. General approach**

For the statistical analysis of lab endpoints, data from enrolled participants will be used according to the initial randomization assignment regardless of how many infusions they received. Additional analyses may be performed, limited to participants who received all scheduled infusions per protocol. Assay results that are unreliable, or from HIV-infected participants postinfection will be excluded. Since the exact date of HIV infection is unknown, any assay data from blood draws 4 weeks prior to an infected participant's last seronegative sample and thereafter may be excluded. If an HIV-infected participant does not have a seronegative sample postenrollment, then all data from that participant may be excluded from the analysis. Assay results that are from specimens collected outside of the visit window are generally also excluded unless otherwise noted in analyses (e.g., population pharmacokinetics analyses of concentrations over time) that account for the actual date of specimen collection.

For continuous assay data (eg, serum concentration of VRC01), graphical and tabular summaries of the distributions by treatment arm and timepoint will be made. Scatterplot matrix with correlation coefficient information between each pair of serum and mucosa drug levels at different timepoints will be provided. An appropriate data transformation (eg, log transformation) may be applied prior to testing to better satisfy analysis assumptions. Inference from these analyses would be limited by the small sample sizes of the groups.

For qualitative assay variables (eg, positive or negative), the analyses will be performed by tabulating the frequency of positive responses for each assay by group at each timepoint at which an assessment is performed. Crude response rates will be presented with their corresponding 95% confidence interval estimates calculated using the score test method [66].

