### 10.2.2. List of Graphs

- Boxplots of baseline mucosal level normalized by total IgG, by sex at birth, tissue type, and treatment arm
- Boxplots of baseline mucosal level normalized by protein, by sex at birth, tissue type, and treatment arm
- Boxplots of baseline mucosal level without normalization, by sex at birth, tissue type, and treatment arm
- Lineplots of baseline and post-infusion mucosal level normalized by total IgG, by sex at birth, tissue type, and treatment arm
- Lineplots of baseline and post-infusion mucosal level normalized by protein, by sex at birth, tissue type, and treatment arm
- Lineplots of baseline and post-infusion mucosal level without normalization, by sex at birth, tissue type, and treatment arm

- Scatterplots of correlation as following:

Cervicovaginal secretions to Cervical homogenates

Cervicovaginal secretions to Vaginal homogenates

Blood to Cervical homogenates

Blood to Vaginal homogenates

Blood to Cervicovaginal secretions

Rectal secretions to rectal homogenates

Rectal secretions to Semen

Rectal secretions to blood

Rectal homogenates to Semen

Rectal homogenates to blood

Rectal homogenates to Cervical lysates

Rectal homogenates to vaginal lysates

Rectal homogenates to cervicovaginal secretions

Rectal secretion to Cervical lysates

Rectal secretion to vaginal lysates

Rectal secretion to cervicovaginal secretions

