### 10.3. Serum VRC01/LS Levels by ELISA

#### 10.3.1. List of Tables

- Summary statistics (i.e., N, N> LLoQ, geometric mean, median, min, max and IQR) of VRC01/LS concentration by visit (number and label), and treatment arm in all participants
- Summary statistics (i.e., N, N> LLoQ, geometric mean, median, min, max and IQR) of VRC01/LS concentration by visit (number and label), and treatment arm among participants who received all infusions
- Summary statistics (N, median and mean +/- SD) of the estimated half-life by treatment group among all participants.
- For Groups 1-3, summary statistics (N, geometric mean, median) of second vs. first, third/first, fourth vs first (if applicable) accumulation in terms of observed trough and observed AUC by treatment group among participants who received all infusions.

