#### 10.3.2. List of Graphs

- Individual time-concentration curves with the geometric mean overlaid by treatment group in all participants.
- Individual time-concentration curves with the geometric mean overlaid by treatment group among participants who received all infusions.
- If needed, the above two sets of figures will be repeated with the median (instead of geometric mean) overlaid.

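### Primary objective 2 is set per sex at birth, but the SAP's serum outputs, mucosal tables and rectal correlations name no sex breakdown; rectal levels by sex are planned only as figures.

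*SAP*

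**What the plan says.** The objective, in SAP 3.1 and identically in protocol 5.1, is "For each sex at birth, to evaluate the pharmacokinetics of VRC01 in serum versus mucosa in each mucosal compartment". Protocol 6.1.2 computes power for the serum-mucosa correlation separately for male and female compartments, and protocol 6.2 stratifies randomization by sex at birth.

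The listed SAP outputs are broken down as follows:

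- **Mucosal tables (10.2.1).** All three are by tissue type, visit and arm. One gives statistics "of VRC01/LS concentration without normalization, by tissue type, visit, and treatment arm".
- **Serum tables (10.3.1).** Concentrations are summarized "of VRC01/LS concentration by visit (number and label), and treatment arm in all participants", and again among those who received every infusion. Half-life statistics are "of the estimated half-life by treatment group among all participants". Accumulation is also by treatment group.
- **Serum curves (10.3.2).** "Individual time-concentration curves with the geometric mean overlaid by treatment group in all participants", and again for those who received every infusion.
- **Correlations.** SAP 8.5.1 promises: "Scatterplot matrix with correlation coefficient information between each pair of serum and mucosa drug levels at different timepoints will be provided". SAP 10.2.2 lists 16 scatterplots, for example "Rectal homogenates to blood", with no sex, arm or visit named.
- **Mucosal level figures (10.2.2).** All six boxplot and lineplot items are by sex at birth. The boxplots show baseline only; the three lineplots include post-infusion levels.

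Protocol 9.6 says who gives rectal samples. Men do. For women: "At the Seattle CRS, female participants will also provide rectal fluids and rectal biopsies, if they agree to do so". A woman who no longer wishes to give cervicovaginal samples may also switch to the rectal compartment.

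**The concern.** Serum is collected from both sexes, and rectal samples can be. Without a sex factor, the serum concentration, half-life and accumulation summaries describe men and women together, and so does any rectal row that contains both. A primary objective framed per sex would then have no serum result by sex, no numeric rectal summary by sex and no rectal-serum correlation by sex.

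The correlations carry a further risk. If men and women differ in mean serum level and in mean rectal level, a pooled correlation reflects that difference as well as the within-person relationship, and can be inflated or hidden by it. Scheduled female rectal sampling takes place only in Seattle, so sex is also partly tied to site.

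Men are the more exposed. The only blood-mucosa plots in 10.2.2 that include them are the two rectal ones. No blood-semen plot is listed there, although the general scatterplot matrix in 8.5.1 could cover that pair.

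**Working it through.** **1. Is the design per sex?** Inputs from protocol 6.1 and 6.1.2: 10 men and 13 women in each of Groups 1 and 2, 8 and 8 in Group 4, and 15% missing laboratory data. With n = floor(0.85 × N per sex):

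- Groups 2+4: men 18 × 0.85 = 15.3, so 15; women 21 × 0.85 = 17.85, so 17.
- Groups 1+2+4: men 28 × 0.85 = 23.8, so 23; women 34 × 0.85 = 28.9, so 28.

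These are Table 6-3 columns. The stated method is power = Φ(√(n−3) × [atanh ρ + ρ/(2(n−1))] − 1.96), two-sided 5%. At ρ = 0.7:

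- n = 15: √12 × (0.8673 + 0.0250) − 1.96 = 1.13, power 87.1% (stated 87%).
- n = 17: √14 × (0.8673 + 0.0219) − 1.96 = 1.37, power 91.4% (stated 91%).

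All 49 cells of the table reproduce within one percentage point. The design figures are therefore sex-specific. (A separate slip: the text attaches power above 94% at ρ = 0.6 to 25 women. That figure belongs to the n = 28 column, 94.1%; n = 25 gives 91.1%.)

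**2. Which outputs can mix the sexes?** Cervical, vaginal and cervicovaginal samples come only from women and semen only from men. Of the 16 scatterplots in 10.2.2, 13 include one of these and so contain one sex. The other three can mix: rectal secretions with rectal homogenates, rectal secretions with blood, and rectal homogenates with blood. Of the five blood-mucosa plots, three are female-only and two are rectal. Every serum table and curve in 10.3 covers both sexes.

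**3. How many women could be in the rectal data?** The documents do not say. After 15% missing, the pooled rectal n in Groups 1+2+4 could run from 23 (no women) to 52 (all women: 62 × 0.85 = 52.7).

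**4. How far could pooling move a correlation?** Neither document gives a sex difference in level, so these are assumptions. Suppose both sexes share the within-sex correlation ρ, means differ by d SD in serum and in rectal level, and a fraction w are women. With v = w(1−w)d², the pooled value is (ρ + v)/(1 + v) if the differences run the same way and (ρ − v)/(1 + v) if they run opposite ways. For ρ = 0.3:

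| d | w | v | same direction | opposite |
|---|---|---|---|---|
| 0.5 | 0.5 | 0.0625 | 0.3625/1.0625 = 0.34 | 0.2375/1.0625 = 0.22 |
| 1 | 0.2 | 0.16 | 0.46/1.16 = 0.40 | 0.14/1.16 = 0.12 |
| 1 | 0.5 | 0.25 | 0.55/1.25 = 0.44 | 0.05/1.25 = 0.04 |

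With no sex difference in either level, pooling leaves the correlation at 0.3.

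**The case against.** Several stronger readings are tempting, and the documents do not support them.

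- *The plan gives no rectal level by sex.* A reader who looked only at the tables might infer this. The 10.2.2 lineplots show post-infusion mucosal levels by sex, tissue and arm, normalized and raw. Only the numbers are missing.
- *All serum-mucosa correlations pool the sexes.* Three of the five blood-mucosa plots are female-only.
- *Every rectal result mixes men and women.* Mixing arises only through consenting Seattle women and compartment switchers. Protocol 6.1 puts Groups 1-3 at different sites from Groups 4-5. The SAP's infectivity section names Seattle and Cape Town for an endpoint limited to Groups 1-3. On that inference, Group 4 rectal data are male unless a woman switches.
- *The SAP says it pools.* It does not; it omits the factor. The scatterplot list is terse enough to omit arm and visit too, and the objective is restated per sex.
- *A large bias is shown.* The 1 SD, equal-numbers case is one hypothetical, and equal numbers is doubtful when female rectal sampling is optional and mainly at one site.

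It is also fair to say that the correlation is described in protocol 6.1.2 as preliminary, and that SAP 8.5.2 will model participant characteristics in a population PK analysis. That analysis is reported separately and does not name sex, so it cannot be counted on to fill the gap.

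What survives is narrower: no listed serum output, no mucosal table and none of the three mixable correlations names sex. The main infectivity summary table in 10.1.1, for a secondary endpoint, is split by sex at birth, which suggests an oversight.

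**Conclusion.** The point holds in narrow form. Objective, stratification and power are all per sex. As listed, the SAP gives no serum result by sex, no numeric rectal summary by sex and no rectal correlation by sex. Single-sex compartments are unaffected, and rectal levels by sex will be seen in figures.

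The missing outputs are certain from the text; the effect on results is not. It depends on sex differences and on a number of female rectal contributors that the documents do not give. A pooled value between 0.04 and 0.44 for a within-sex 0.3 is the span of the assumed cases, not an estimate. Data collection, randomization and sample size are not in question. The change is worth making because it is cheap and aligns the outputs with a primary objective.

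**What to change.** For the VRC01 groups (1, 2 and 4):

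- add sex at birth to the 10.3.1 tables, the 10.3.2 curves and the rectal rows of the 10.2.1 tables;
- report by sex the correlations of rectal secretions with blood, rectal homogenates with blood, and rectal secretions with rectal homogenates;
- give any pooled rectal-serum correlation as sex-adjusted (partial), and state how many women contribute.

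For the VRC01LS groups (7 and 10 participants in the SAP schema), by-sex listings are enough. The 13 single-sex scatterplots need no change.

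The cost is SAP wording and programming, with no new samples. The downside is smaller cells. For serum, and for male rectal data, they are the sizes Table 6-3 already assumes: at ρ = 0.7 a single arm gives 53.6% power for 8 men in Group 1 or 2. Table 6-3 does not cover female rectal data, whose n is limited to consenting Seattle women and switchers, so those results should be presented as descriptive.

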### 10.2.2. List of Graphs

- Boxplots of baseline mucosal level normalized by total IgG, by sex at birth, tissue type, and treatment arm
- Boxplots of baseline mucosal level normalized by protein, by sex at birth, tissue type, and treatment arm
- Boxplots of baseline mucosal level without normalization, by sex at birth, tissue type, and treatment arm
- Lineplots of baseline and post-infusion mucosal level normalized by total IgG, by sex at birth, tissue type, and treatment arm
- Lineplots of baseline and post-infusion mucosal level normalized by protein, by sex at birth, tissue type, and treatment arm
- Lineplots of baseline and post-infusion mucosal level without normalization, by sex at birth, tissue type, and treatment arm

- Scatterplots of correlation as following:

Cervicovaginal secretions to Cervical homogenates

Cervicovaginal secretions to Vaginal homogenates

Blood to Cervical homogenates

Blood to Vaginal homogenates

Blood to Cervicovaginal secretions

Rectal secretions to rectal homogenates

Rectal secretions to Semen

Rectal secretions to blood

Rectal homogenates to Semen

Rectal homogenates to blood

Rectal homogenates to Cervical lysates

Rectal homogenates to vaginal lysates

Rectal homogenates to cervicovaginal secretions

Rectal secretion to Cervical lysates

Rectal secretion to vaginal lysates

Rectal secretion to cervicovaginal secretions

### 10.3. Serum VRC01/LS Levels by ELISA

#### 10.3.1. List of Tables

- Summary statistics (i.e., N, N> LLoQ, geometric mean, median, min, max and IQR) of VRC01/LS concentration by visit (number and label), and treatment arm in all participants
- Summary statistics (i.e., N, N> LLoQ, geometric mean, median, min, max and IQR) of VRC01/LS concentration by visit (number and label), and treatment arm among participants who received all infusions
- Summary statistics (N, median and mean +/- SD) of the estimated half-life by treatment group among all participants.
- For Groups 1-3, summary statistics (N, geometric mean, median) of second vs. first, third/first, fourth vs first (if applicable) accumulation in terms of observed trough and observed AUC by treatment group among participants who received all infusions.

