VRC 602 (NCT01993706) is titled, “*A Phase 1 Dose-Escalation Study of the Safety and Pharmacokinetics of a Human Monoclonal Antibody, VRC-HIVMAB060-00-AB (VRC01), Administered Intravenously or Subcutaneously to Healthy Adults.*”

VRC 602 was the first study of the VRC01 mAb in HIV-uninfected adults. It was a dose-escalation study to examine safety, tolerability, dose, and PK of VRC01. VRC 602 opened in December 2013 as a single site study at the NIH Clinical Center, Bethesda, Maryland and the final infusion was administered in August 2014.

As shown in [Table 4-8](#), there were 3 open-label, dose escalation groups (Groups 1, 2, and 3) for IV administration and 1 double-blinded, placebo-controlled group (Group 4) for SC administration.

Table 4-8 VRC 602 study schema

VRC 602 Groups			VRC01 Administration Schedule	
Group	Initial Enrollments	Additional Enrollments	Day 0	Week 4
1	3	2	5 mg/kg IV	5 mg/kg IV
2	3	2	20 mg/kg IV	20 mg/kg IV
3	3	2	40 mg/kg IV	40 mg/kg IV
4	SC administration			
4A	3	2	5 mg/kg SC	5 mg/kg SC
4B	3	2	Placebo SC	Placebo SC
Total		25	20 participants treated with VRC01 at different dosage levels and 5 participants treated with placebo administered SC	
IV doses administered in 100 mL of normal saline over 1 hr. First SC dose administered at about 15 mL/hr via SC infusion pump; subject option for second dose administration (Week 4) by direct SC injection with needle and syringe.				

All IV and/or SC infusions were well-tolerated with no SAEs or dose limiting toxicity.

PK analysis from VRC 602 revealed a VRC01 terminal half-life of 15 days across all IV infused dose groups. Trough levels are shown in [Table 4-9](#) below.

Table 4-9: Trough levels 28 days post first and second infusion

Time	Dose	
	20 mg/kg	40 mg/kg
28 days post infusion #1	35 mcg/ml	57 mcg/ml
28 days post infusion #2	57 mcg/ml	89 mcg/ml

4.7.1.3 HVTN 104

HVTN 104, titled *A phase I clinical trial to evaluate the safety and drug levels of a human monoclonal antibody, VRC-HIVMAB060-00-AB (VRC01) administered in multiple doses intravenously and subcutaneously in different dosing schedules to healthy, HIV-uninfected adults*, is examining safety profiles and serum levels of 5 different regimens for the IV and SC administration of VRC01 ([Table 4-10](#)). IV administration is being evaluated at doses of 10, 20, 30, and 40 mg/kg; SC administration is being tested at 5 mg/kg.

Table 4-10 HVTN 104 study schema

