10.3 Drug detection and quantitation

10.3.1 VRC01/VRC01LS mAb levels in serum, mucosal tissue lysates and mucosal secretions

VRC01/VRC01LS levels will be measured in serum, semen, cervicovaginal secretions, rectal secretions, and mucosal tissue lysates prepared from cervical, vaginal and rectal biopsies collected at the designated timepoints. A quantitative assay (such as an ELISA), binding multiplex antibody assay (BAMA), or Singulex assay may be used to determine the concentration of VRC01/VRC01LS in the aforementioned samples and/or to assess their binding to various Env proteins, such as Consensus gp120, Consensus gp140 and CD4 binding site proteins. ELISA assays employing two different antigens may be used for VRC01/VRC01LS quantitation. One assay employs the resurfaced core 3 antigen (RSC3), designed for selective detection of CD4 binding site bNAbs, such as VRC01/VRC01LS (46). The other assay employs the VRC01 Fab-specific 5C9

mAb, which is an anti-idiotypic antibody cloned from a single B cell that was sorted by flow cytometry using a VRC01 scFv probe. The operational sensitivity of the BAMA and ELISAs with respect to the various sample specimens will be determined for the clinical grade VRC01/VRC01LS mAbs used for this study. However, ongoing studies currently indicate that the interim lower LOD for VRC01 mAb is $\leq 129 \pm 30$ ng/ml, 125 ± 22 ng/ml, and 93 ± 14 ng/ml in serum, semen, and saliva, respectively, using RSC3 protein on the BAMA platform (with validated plasma LOD of 2.3 -8.0 ng/ml). The LOQ of the validated ELISA using the VRC01 Fab-specific 5C9 mAb is currently 1.1 mcg/mL in serum. The Singulex assay combines a proprietary digital Single Molecule Counting (SMC) technology with a robust microparticle-based immunoassay utilizing the mAb 5C9 to provide higher sensitivity (lower limit of quantification = 50 pg/mL) and broad dynamic range. As the technology for all of these assays continues to develop, an updated assay(s) may be utilized. Any assay that may be used for this study will first be qualified, at a minimum, for linearity, precision, and accuracy.

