##### **Duration per participant**

As VRC01LS is designed to have a longer half-life than VRC01, participants who receive VRC01 will be followed for 6 months after the last product administration and participants who receive VRC01LS will be followed for 12 months after the last product administration. Specifically,

Groups 1, 2, and 5: 12 months of scheduled clinic visits

Group 3: 18 months of scheduled clinic visits

Group 4: 6 months of scheduled clinic visits

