### **Singulex assay for mucosal VRC01/VRC01LS Levels**

VRC01/LS concentrations will be calibrated via a 5PL model of the standard samples on the same plate. The machine Erenna detects single molecules of VRC01/VRC01LS as photons over a read time. Each measurement of photons above a threshold is considered a detected event and the sum of all photons from these events over the read time (i.e. signal intensity) is called the event photon (EP) measurement for the sample or standard. The EP curve of the VRC01/LS standard will be used to calibrate the VRC01/VRC01LS concentrations in mucosal and serum samples. The lower limit of quantitation (LLoQ) of each run is defined by the lowest standard maintaining less than or equal to 20% coefficient of variation (CV). The estimation of the standard curve and the calibration of study samples will be carried out using the nCal package in R (Fong et al., Biometrics, 2012; Fong et al., Bioinformatics, 2013).

Graphical and tabular summaries of the distributions of VRC01/LS mucosal levels normalized by total IgG/protein, as well as levels data without normalization will be made for each biopsy type, treatment arm, and time point. Correlation plots will be generated between different sample types.

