### **ELISA for VRC01/VRC01LS Levels in Serum**

Concentration values below the limit of quantification ( $=1.0$  ug/ml) will be replaced by  $0.5$  ug/ml in all calculations. Spaghetti plots will be used to display each participant's time-concentration curves, with the treatment group geometric mean or median overlaid. The geometric mean as well as the median and inter-quartile ranges will be used to summarize the drug level at each time-point by treatment group in a summary table.

Individual-level non-compartmental pharmacokinetics (PK) analysis will be performed. Specifically, for Groups 1-3, we will compute drug accumulation based on the ratio of observed trough drug level measurements and the area under the observed time-concentration curve (AUC) for each participant, after the second, third and fourth (Groups 1 & 2 only) infusions as compared to the first. We will report the mean, median, and standard deviation (SD), in addition to the listing of individual values. AUC will be calculated based on raw (not log-transformed) data using the linear trapezoidal method. The actual visit dates will be used in these AUC calculations.

Lastly, for each participant in Groups 1-5, the terminal elimination rate and half-life will be calculated based on the log-linear portion of the time-concentration curve after the last infusion. The terminal rate (slope) will be determined by fitting a linear regression line over the log-transformed concentrations over the actual visit date (in days). The half-life is estimated as  $\log(2)$  divided by the terminal slope. The effect of participants' characteristics on various PK parameters and inter-individual variabilities of these parameters will be modeled via population compartmental pharmacokinetics analysis and reported separately.

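### All listed serum summaries use an ELISA expected to be below its limit at Month 6, so every VRC01 arm's final-visit summary would show the substituted 0.5 ug/mL

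*SAP*

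**What the plan says.** - **Endpoint.** SAP 3.1 (as in protocol 5.1) defines the serum part of primary endpoint 2, for Groups 1, 2 and 4, as "Serum concentration of VRC01 out to Month 6 after the last infusion". Follow-up is set to match: "participants who receive VRC01 will be followed for 6 months after the last product administration".
- **Serum outputs.** The listed serum tables (10.3.1) and time-concentration curves (10.3.2) all fall under "Serum VRC01/LS Levels by ELISA". The concentration tables give N, N above the limit, geometric mean, median, range and IQR by visit and arm. The curves carry the geometric mean, or the median if needed.
- **ELISA limit.** SAP 8.5.2 sets it at 1.0 ug/mL. The rule opens "Concentration values below the limit of quantification" and replaces such values with 0.5 ug/mL throughout. Protocol 10.3.1 has a slightly different figure: "The LOQ of the validated ELISA using the VRC01 Fab-specific 5C9 mAb is currently 1.1 mcg/mL in serum".
- **Singulex.** Protocol 10.3.1 gives this assay a "lower limit of quantification = 50 pg/mL". SAP 8.5.2 says its standard curve "will be used to calibrate the VRC01/VRC01LS concentrations in mucosal and serum samples". The summaries it then promises cover mucosal levels, plus correlation plots between sample types.
- **Blood-mucosa plots.** These are listed in SAP 10.2.2, under the mucosal heading, and the assay used for blood is not named. SAP 8.5.1 also promises correlations between serum and mucosal levels at different timepoints, again without naming the serum assay.

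**The concern.** The endpoint's horizon and the assay's range do not appear to meet. If serum VRC01 is far below 1.0 ug/mL by Month 6, the listed tables will print the substituted value, not a concentration, for a primary endpoint at its last visit. A geometric mean of about 0.5 ug/mL in both the 10 and 30 mg/kg arms could be read as a measured level with no dose effect. The final visit is also a biopsy visit, where mucosal drug is read by a much more sensitive assay, so how long drug persists in mucosa relative to serum is asked most directly there.

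**Working it through.** **Inputs**
- Half-life 15 days, protocol 4.7.1.2: "PK analysis from VRC 602 revealed a VRC01 terminal half-life of 15 days across all IV infused dose groups".
- HVTN 104 mean troughs 56 days after infusion, protocol 4.7.1.3: 10 mg/kg, 4.1 then 2.5 ug/mL; 30 mg/kg, 10.4 then 11.5 ug/mL.
- Final visit, Groups 1 and 2 (Visit 17, Appendix L): D351-365, last infusion D168, so 183-197 days after it.
- Final visit, Group 4 (Visit 14, Appendix N): 169-183 days after the only infusion.
- Visit 16, Groups 1 and 2: D253-267, so 85-99 days after the last infusion. Visit 12, Group 4: 127-141 days.

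**Check of the stated half-life.** HVTN 104 reports 75.6 ug/mL at day 28 (its Group 1) and 20.1 at day 56 (its Group 2), both after a first 40 mg/kg dose. Then 28 × ln 2 / ln(75.6/20.1) = 14.7 days, which agrees with 15.

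**Projection.** C(t) = C(56) × 2^(−(t−56)/15), starting from 4.1 (Group 1), 11.5 (Group 2) and 10.4 (Group 4).

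| Arm and visit | Days after last infusion | Expected serum, ug/mL |
|---|---|---|
| Group 1, Visit 16 | 85-99 | 1.07-0.56 |
| Group 1, Visit 17 | 183-197 | 0.012-0.006 |
| Group 2, Visit 16 | 85-99 | 3.0-1.6 |
| Group 2, Visit 17 | 183-197 | 0.033-0.017 |
| Group 4, Visit 12 | 127-141 | 0.39-0.21 |
| Group 4, Visit 14 | 169-183 | 0.056-0.029 |

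Starting Group 1 from the second trough, 2.5, gives 0.007-0.004 at Visit 17. Mean levels cross 1.0 ug/mL at 56 + 15 × log2(C(56)) days: about day 87 in Group 1, 109 in Group 2 and 107 in Group 4.

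**Size of the distortion at the final visit.** For 30 mg/kg, 0.5/0.056 = 8.9 and 0.5/0.017 = 29. For 10 mg/kg, 0.5/0.012 = 42 and 0.5/0.006 = 83.

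**Sensitivity to half-life**
- At 12 days, no final-visit mean exceeds 0.02 ug/mL. At 20 days, the highest is 10.4 × 2^(−113/20) = 0.21 (Group 4).
- Half-life needed to reach 1.0 on the earliest final-visit day: 113/log2(10.4) = 33 days (Group 4), 127/log2(11.5) = 36 (Group 2), 127/log2(4.1) = 62 (Group 1).
- With assumed between-person CVs of 20-40% on half-life and 50% on the day-56 level, fewer than 3% of participants in any arm exceed 1.0. The geometric mean would then sit close to 0.5, and the median at 0.5.

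**Would Singulex reach these levels?** On the stated limits it is 1,000,000/50 = 20,000 times more sensitive than the ELISA. Expected final-visit levels of 0.004-0.056 ug/mL (3,700-56,000 pg/mL before rounding) are about 75 to 1,100 times its limit.

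**The case against.** The strongest reply is that the SAP already has a sensitive serum assay and probably uses it where it matters. Section 8.5.2 normalises serum together with secretions and tissues, says the Singulex curve calibrates serum, and promises correlation plots between sample types. Every blood-mucosa scatterplot is listed under 10.2, the mucosal section, and none under the ELISA section. The natural reading is that those plots use Singulex blood. This stands. A reader might infer that constant ELISA values will be paired with Singulex mucosa and that the serum-mucosa comparison is lost. The documents specify no such pairing, and no serum-mucosa concentration ratio is planned. What remains is that the blood assay is not named.

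It is also fair to say that the endpoint is a profile to Month 6, not a single Month 6 value. A profile that ends below quantification is an ordinary PK result, and the accumulation analyses concern the dosing period, where expected troughs exceed the limit. So it would be too strong to call the endpoint undeliverable, or to say that all arms fail at every late biopsy visit. Group 2 remains quantifiable at Visit 16, and Group 1 is only borderline there.

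N above the limit is tabulated, so the censoring would be visible. But that does not recover a concentration, and the adjacent geometric mean would still be wrong.

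Finally, the half-life could be longer. VRC 602 troughs rise from 35 to 57 and from 57 to 89 ug/mL after a second dose at 4 weeks. Under a mono-exponential model these imply 42 and 34 days. At 42 days Groups 2 and 4 would be just quantifiable (1.1-1.4 and 1.3-1.6) and Group 1 would not (0.4-0.5). That reading conflicts with the 15 days stated for the same study, and HVTN 104 accumulation at 30 and 40 mg/kg gives 17 and 14 days.

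**Conclusion.** The point holds for the listed serum summaries. At the final visit the ELISA geometric mean and median are expected to read about 0.5 ug/mL in Groups 1, 2 and 4. True means are expected to be at least about 18 times below the 1.0 limit (1.0/0.056), and the substituted value hides the dose difference. Group 4 is also expected below the limit at Visit 12.

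This rests on the protocol's 15-day half-life, mono-exponential decline and the HVTN 104 troughs. The documents give no VRC01 level beyond 56 days after an infusion, so the exact values are extrapolated. The direction is secure unless the half-life is about twice the stated figure or more. Nothing was computed for the VRC01LS arms.

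The gap is a missing Singulex serum summary, an unnamed blood assay in the correlations, and a substitution rule applied where almost everything is censored. The sensitive assay itself is not missing, and the primary endpoint need not be redefined.

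**What to change.** 1. In SAP 10.2 or 10.3, add a serum concentration table and curve by visit and arm from the Singulex assay. Present it as a separate, complete series beside the ELISA, not spliced in below 1.0 ug/mL, which could put an assay step into the curve. Include an agreement check in the range where both assays quantify. The check is needed because the 50 pg/mL limit is not stated specifically for serum.
2. In SAP 10.2.2, and for the serum-mucosa correlations in 8.5.1, state that blood values are Singulex and that substituted ELISA values are never used.
3. In SAP 10.3, where most ELISA values at a visit are below the limit, report the number and percent below it and give the summary as <1.0 ug/mL, with no geometric mean built on 0.5. Reconcile the 1.0 and 1.1 limits at the same time; the difference does not affect the result.

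Cost: SAP wording, extra tables, the agreement check and possibly Singulex runs on stored late-visit serum if these have not been done. The documents do not say which visits have Singulex serum. Item 3 needs no assay work.
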